the difference in hippocampal shape between the two groups was evaluated using eigenvectors derived from the HDBM-LD transformations (see Research Design and Methods for further explanation). The first 20 eigenvectors explained 87.5% of the variance in hippocampal shape, and a MANOVA using these variables revealed a significant group difference ($F = 3.34$, $df = 20,90$, $p < .0001$). Moreover, in a "leave-one-out" (jackknife) discriminant function analysis, 56 of the 65 non-demented subjects (86% sensitivity) and 36 of 46 DAT subjects could be correctly classified (78% specificity). In this study, the group discrimination achieved by hippocampal shape information alone was equivalent to the discrimination achieved when both hippocampal volume and shape information was used. Not surprisingly, eigenvector 1 was correlated with both left ($\rho = .69$, $p < .0001$) and right ($\rho = .69$, $p < .0001$) hippocampal volumes.

The pattern of hippocampal shape abnormality found in these DAT subjects (see Figure 1) was highly similar to the pattern of deformity we observed in our first study (Csernansky, et al, 2000), and again showed inward deformation of the head and lateral prominence of the hippocampus. This pattern of hippocampal deformation is highly consistent with patterns of plaque and tangle deposition in the CA1 hippocampal subfield observed in post-mortem studies of AD (Arnold, et al, 1991; Price and [name], 1999).

Assessment of Disease Progression Using Neuroanatomical Markers

During the first funding period, we completed a longitudinal study comparing changes in hippocampal structure in CDR 0.5 and CDR 0 subjects matched for age and gender over approximately two years (mean interval in years (range) - CDR 0.5 – 2.0 (1.0-2.6) and CDR 0 subjects– 2.2 (1.4-4.1) (Wang, et al, 2003). The results of this study are critical for this application, as they demonstrate that our approach to assessing disease progression can discriminate between subjects with and without DAT, and so may also be sensitive to differences between groups of DAT patients treated with different drugs. This study included 18 CDR 0.5 subjects and 26 CDR 0 subjects that were partially overlapping with the subjects included in our previously published cross-sectional study (Csernansky, et al, 2000). The 18 CDR 0.5 subjects were not treated with cholinesterase inhibitors or memantine during the period of study. Measures of hippocampal shape and

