volume were generated across both groups and time as in the cross-sectional study. At baseline, the CDR 0 subjects had a mean (SD) hippocampal volume of 2081(354) mm³ on the left side and 2600 (481) mm³ on the right side, while the CDR 0.5 subjects had a mean hippocampal volume of 1717 (224 mm³) on the left side and 2186 (370 mm³) on the right side. At follow-up, the CDR 0 subjects showed a hippocampal volume reduction of 82 mm³ on the left side and 142 mm³ on the right side, while the CDR 0.5 subjects showed a hippocampal volume reduction of 164 mm³ on the left side and 236 mm³ on the right side. ANOVA indicated a significant group effect on the rate of hippocampal volume loss ($F = 7.81$, $df = 1,42$, $p = 0.008$). This difference persisted after covarying hippocampal volumes for total cerebral brain volume ($p = 0.007$), total intra-cranial volume ($p = 0.008$) and scan interval ($p = 0.015$).

[figure not shown]

Figure 2. Comparisons from Baseline to Follow-up (two years) in CDR 0.5 and CDR 0 Elder Subjects. Displacement maps were used to visualize the across-time difference in hippocampal structure in the two subject groups. Cooler colors (blue to purple) signify areas of inward deformation over time. In the CDR 0.5 subjects, areas of inward deformation were more widespread and included more of the lateral edge of the hippocampus, while in the CDR 0 subjects, areas of inward deformation were smaller and confined to the head

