For the testing of **Hypothesis 2**, we will be measuring the rate of change of neuroanatomical variables over time; therefore, the test-retest reliability for these variables must be high. To estimate the normative test-retest reliability of the neuroanatomical measures proposed in this application, we scanned eight healthy control subjects on two separate occasions approximately one month apart, and then estimated differences between volumes and surface contours of the hippocampus. At the first time point, the mean left hippocampal volume was 2,233 mm³ and the mean right hippocampal volume was 2,699 mm³; at the second time point, these volumes were 2,209 and 2,686 mm³, respectively. Using repeated measures ANOVA, there were no significant test-retest differences in these volumes (on the left $F = .14$, $p = .72$; on the right $F = .07$, $p = .80$) and the intraclass correlation coefficient between these two datasets was very high (ICC = 0.93). To compare the similarity of surface contours at the two time points, we then registered all the scans with respect to the template and then calculated the percent overlap of voxels. The average percent overlap in the eight subjects was 87.4%, which is comparable to the overlap achieved by a single expert performing repeated manual segmentations of the hippocampus from the same MR scan (Haller, et al, 1997). To test the reliability of shape assessment for the hippocampus, we generated the eigenvectors associated with this brain structure based on the eight control subjects at time point 1. The coefficients associated with these eigenvectors were then computed for each subject at both time 1 and time 2. The mean ICC for all eigenvector coefficients was very high - 0.89 (range of 0.83 to 0.94), suggesting very high repeatability. Finally, the standard deviation for the estimation of hippocampal volumes on the two occasions was 225 mm³, and an annual rate of decrease in hippocampal volumes was 2 mm³.

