Assuming that the between-group effect size for comparisons of the rate of change of neuroanatomical variables is moderate (i.e., 0.5 or higher), and if the correlations in neuromorphometric measures within our proposed sample sizes at the different time points continue to be high (i.e., > .75), changes in brain structure shapes of the magnitude observed to date (see Progress Report and Wang, et al, 2003), and volume decreases of 50 mm³ or greater over two years, would be detectable with greater than 85% power (Borenstein and Cohen, 1988; Kraemer and Thiemann, 1987).

HUMAN SUBJECTS

50 new subjects who meet NINDS-ADRDA criteria for probable AD (i.e. DAT), and who have been registered with the MDC for treatment will be recruited for participation in the project during the proposed

funding period. The age range of the subjects will be 50 to 80 years. Any subjects will be excluded if they have medical problems that would contraindicate treatment with donepezil or memantine or make administration of a MR scan or any other aspect of the protocol hazardous.

With regard to the inclusion of both genders and various minorities, the samples will be equally balanced for gender and include approximately 15% African-American subjects. This percentage is similar to the distribution of African-Americans who present to the ADRC and MDC. This distribution of subjects should also allow inclusion of gender as a covariate in data analyses.

2. Collected clinical data will include information about demographics, dementia symptoms, other behavioral disturbances, and performance on tests of cognition (i.e., the ADAS-Cog). In all cases, verbal or written information obtained directly from the patients and involved caregivers will be used. These evaluations will take place in an ordinary office setting. MR scan data will be collected according to established protocols at the Mallinckrodt Institute of Radiology at Washington University.

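### The 2 mm³ per year hippocampal loss is unsourced and does not fit the protocol's own longitudinal data; separately, the power above 85% for 50 mm³ is not delivered for the between-group comparisons of Hypothesis 2

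*Combined protocol and SAP*

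**What the plan says.** Section i (Sample Size and Power Considerations) supports Hypothesis 2 with a reliability study: "we scanned eight healthy control subjects on two separate occasions approximately one month apart". At the first scan "the mean left hippocampal volume was 2,233 mm³ and the mean right hippocampal volume was 2,699 mm³"; at the second the means were 2,209 and 2,686 mm³. The paragraph reports an ICC of 0.93 and closes with an SD of 225 mm³ and the words "an annual rate of decrease in hippocampal volumes was 2 mm³". It does not say in whom, on which side or from what source.

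The next paragraph gives the power. It assumes a between-group effect size of at least 0.5 and a correlation between time points above .75, and concludes that "volume decreases of 50 mm³ or greater over two years, would be detectable with greater than 85% power". It names no test, significance level, sidedness or group sizes for Hypothesis 2.

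Under Assessment of Disease Progression Using Neuroanatomical Markers, the protocol reports its own longitudinal study, with mean scan intervals of 2.0 years (CDR 0.5, n = 18, untreated) and 2.2 years (CDR 0, n = 26). At follow-up, "the CDR 0.5 subjects showed a hippocampal volume reduction of 164 mm³ on the left side and 236 mm³ on the right side", and "the CDR 0 subjects showed a hippocampal volume reduction of 82 mm³ on the left side and 142 mm³ on the right side". The group test on the rate of volume loss was F = 7.81 on 1 and 42 df, p = 0.008.

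Section a (Overall Design and Source of Subjects) gives 21 subjects in Group 1, 38 to 47 in Group 2 and about 40 analysable in Group 3.

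**The concern.** Hypothesis 2 is about slowing a rate of tissue loss. The only annual rate in its power section implies 4 mm³ over the two-year study, while the losses the protocol has already observed are 82 to 236 mm³. A reader of that section cannot tell what share of atrophy a 50 mm³ difference represents.

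The power figure matters more for interpretation. If power for 50 mm³ is well below 85%, a null result for the combination group could be misread as adequately powered evidence that memantine does not slow atrophy.

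**Working it through.** **1. The 2 mm³ per year against the protocol's data** (loss divided by mean interval)

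| Group | Left | Right |
|---|---|---|
| CDR 0.5, untreated | 164/2.0 = 82 | 236/2.0 = 118 |
| CDR 0 | 82/2.2 = 37 | 142/2.2 = 65 |

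Divided by 2, these are 41 and 59 times the stated rate in CDR 0.5, and about 19 and 32 times in CDR 0.

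The reliability sample cannot supply the figure either. Its means fell by 2,233 − 2,209 = 24 mm³ and 2,699 − 2,686 = 13 mm³ in about a month. The reported F values (.14 and .07) imply standard errors of 24/√.14 = 64 and 13/√.07 = 49 mm³ for that change. A rate of 2 mm³ per year is 0.17 mm³ per month.

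**2. Trying to reproduce the power above 85%**

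The method is a two-sample t test on change scores (noncentral t) at two-sided 0.05, which the protocol states only for Hypothesis 1 and is assumed here. Group 3 has n = 40. The standardised effect is d = 50 / SD of change. The SD of change comes from two sources:

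- Section i: 225 × √(2(1 − r)). With r = .75 this is 159 mm³; with r = .93 (the one-month ICC) it is 84 mm³.
- The longitudinal F: difference in loss / (√7.81 × √(1/18 + 1/26)), where the denominator is 2.795 × 0.3066 = 0.857.
  - Raw losses, mean of sides: ((164 − 82) + (236 − 142))/2 = 88, and 88/0.857 = 103 mm³.
  - Annualised first: 100 − 50.9 = 49.1 per year, or 98.2 over two years, and 98.2/0.857 = 115 mm³.

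| Reading | d | v Group 2, n = 47 | v Group 2, n = 38 | v Group 1, n = 21 | One-sample, n = 40 |
|---|---|---|---|---|---|
| d = 0.5 on change scores | 0.50 | 0.63 | 0.59 | 0.45 | 0.87 |
| 50 mm³, SD 225, r = .75 | 0.31 | 0.30 | 0.28 | 0.21 | 0.49 |
| 50 mm³, SD 225, r = .93 | 0.59 | 0.78 | 0.74 | 0.58 | 0.96 |
| 50 mm³, SD of change 103 | 0.49 | 0.61 | 0.56 | 0.43 | 0.85 |
| 50 mm³, SD of change 115 | 0.44 | 0.52 | 0.48 | 0.36 | 0.77 |
| 0.5 × 225 = 112.5 mm³, r = .75 | 0.71 | 0.90 | 0.87 | 0.73 | 0.99 |

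No two-sided comparison of Group 3 with Group 2 or Group 1 reaches 85% for 50 mm³. Using one side only, the implied SD is 96 (left) or 110 (right), and power against Group 2 is 0.51 to 0.67. About 85% appears in three ways:

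- a one-sample within-group test, on some of the SDs;
- a one-sided test with r = .93 and 40 v 47 (0.86);
- reading 0.5 in raw SD units with r = .75, which means 112.5 mm³.

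**3. What 85% power would detect**

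The required d is 0.65 (v 47), 0.69 (v 38) and 0.82 (v 21). Multiplying by SDs of 103 and 115 gives about 67 to 79 mm³ against Group 2 and 84 to 94 mm³ against Group 1. The untreated CDR 0.5 loss over two years is (164 + 236)/2 = 200 mm³. So these are 33 to 39% and 42 to 47% slowing, while 50 mm³ is 25%.

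**The case against.** A reader might infer that 2 mm³ per year is the planning rate, so that the 50 mm³ target has no anchor and no drug could achieve it. The documents do not support that. The power statement lists its inputs and the 2 mm³ is not among them, so deleting it changes no power figure. It closes a paragraph on healthy controls of unstated age and may describe them, in which case it is not strictly in conflict with the CDR 0.5 data. The 50 mm³ is also not arbitrary in size: it is 0.44 to 0.49 of the implied SD of change, near the stated 0.5, and lies below the observed 82 and 94 mm³ differences between CDR 0.5 and CDR 0. What remains is that the plan shows no derivation for it. The healthy-control reading does not rescue the 2 mm³ itself, since nondemented elders lost 19 to 32 times as much.

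It can also be said that the sentence speaks of volume decreases, not treatment differences, and that a within-group test of 40 subjects with SD 103 does give 0.85. The arithmetic is right. But the same sentence assumes a between-group effect size, and Hypothesis 2 compares groups, so that reading does not deliver the claim.

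Pooling Groups 1 and 2 (59 to 68 subjects), which the hypothesised equality might suggest, gives at most 0.84 two-sided, and that with r = .93. A one-sided test would then pass (0.89 to 0.91), but the plan states neither step, and .93 is a one-month reliability in healthy people.

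The implied SD is uncertain. It assumes that F refers to the mean of sides, depends on how unequal intervals were handled, and comes from a sample without CDR 1 or treated subjects. That is why a range is given. The section's own SD with r = .75 is less favourable still.

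**Conclusion.** The concern holds as two separate faults.

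- **The rate.** The 2 mm³ per year is unsourced, does not fit the protocol's longitudinal data and cannot come from eight people scanned a month apart. Taken alone it is a reporting fault that alters no sample size, power figure or analysis. Whether it is a unit slip or belongs to another population cannot be settled from the documents.
- **The power.** The figure above 85% for 50 mm³ is wrong as written for Group 3 against Group 2 or Group 1. At two-sided 0.05 it is about 0.48 to 0.61 and 0.36 to 0.43 with an SD of change of 103 to 115 mm³, 0.28 to 0.30 and 0.21 with SD 225 and r = .75, and at most 0.78 with r = .93.

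The assumptions are the alpha carried over from Hypothesis 1, 40 analysable subjects in Group 3, a t test on difference scores, and the implied SD described above. Section h (Data Analysis) plans Wilcoxon rank sum tests, which would have slightly less power if the change scores are normal.

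**What to change.** - Remove the 2 mm³ per year, or give its source, population, side and unit. The CDR 0.5 rates should not simply be substituted into that sentence: it ends a paragraph on healthy controls, and the documents do not show what the figure was meant to be.
- Cite the longitudinal CDR 0.5 losses separately as the reference rate for Hypothesis 2: 164 and 236 mm³, or about 200 mm³ over two years as the mean of sides.
- Restate power, or the detectable difference, for Group 3 against Group 2 and for Group 3 against Group 1. Give the actual group sizes, test, alpha, sidedness and SD of change, show where the target comes from, and express it also as percent slowing. With SD 103 to 115, 85% power corresponds to about 67 to 79 mm³ (33 to 39%) and 84 to 94 mm³ (42 to 47%).

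This is a rewrite of part of section i. It needs no extra patients. Its cost is that the stated power becomes less favourable, particularly against the untreated group.

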There was also a group difference in the rate of progression of hippocampal shape deformity. The first 12 eigenvectors explained 75% of the variance in hippocampal shape, and using these 12 eigenvectors as variables in a MANOVA, we found a significant group effect ($F = 2.66$, $df = 12,31$, $p = 0.014$; effect size = 2.0). In a follow-up logistic regression analysis, the combination of eigenvectors 1, 2, 4, and 11 were found to be optimally useful for discriminating the patterns of hippocampal shape change in the two groups of subjects ($\chi^2 = 19.4$). Using these four eigenvectors, a significant group x time interaction was found ($F = 7.81$, $df = 4,39$, $p < 0.008$), and in a “take-one-out” discriminant function analysis, 22 out of 26 (84.6%) CDR 0 subjects and 15 out of 18 (83.3%) CDR 0.5 subjects were correctly classified. When hippocampal volume change was included in this logistic regression analysis, only eigenvectors 2, 4, and 11 were selected ($\chi^2=20.1$) (eigenvector 1 was again correlated with the change in hippocampal volume across subject groups - $r = -0.75$, $p < 0.0001$). Visualization of the changes in the shape of the hippocampus in the two groups revealed that areas of inward deformities over time were more widespread in the CDR 0.5 than in the CDR 0 subjects (see Figure 2).

Hippocampal Shape Predicts Response to Donepezil

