The quantification of hippocampal volume and shape using HDBM-LD begins with superimposing a triangulated graph of points onto the gray matter surface of the hippocampus within the template using a computer aided design program for fitting closed surfaces to connected subvolumes. This surface is then treated as a two-dimensional closed manifold and carried along as the template is transformed onto the target MR scans. When the transformations are completed, a vector field and the surface that it represents are generated for each selected brain structure in each of the target scans. Composite surfaces for each structure in each group of subjects are then produced by averaging the individual vector fields generated by the

[figure not shown]
transformations. Brain structure volumes are measured in the subject groups by calculating the gray matter volumes enclosed by the transformation-generated surfaces. Quantification of hippocampal shape is performed using the deformation vector fields produced by the transformations. A pooled covariance matrix is first computed using the vector fields from the transformed surfaces in all subjects. This covariance matrix is then reduced in its dimensionality by computing the complete orthonormal set of eigenvectors, and a subset of eigenvectors that accounts for ~75 % of the variance in hippocampal shape is used in group comparisons.

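### The >85% power figure for hippocampal shape rests on a DAT-versus-nondemented distance, so it is not a power for the drug contrasts in Hypothesis 2

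*Combined protocol and SAP*

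**What the plan says.** Section i (Sample Size and Power Considerations) turns to Hypothesis 2 in its last two paragraphs. It assumes that the "between-group effect size for comparisons of the rate of change of neuroanatomical variables is moderate (i.e., 0.5 or higher") and that measures at the two time points correlate above 0.75. It concludes that "changes in brain structure shapes of the magnitude observed to date", along with volume decreases of at least 50 mm³ over two years, "would be detectable with greater than 85% power". For the shape magnitude it refers to the Progress Report and the group's 2003 longitudinal study. It gives no number for that magnitude, and no alpha, group sizes or eigenvector count for this calculation.

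The 2003 study is described under Preliminary Studies (Assessment of Disease Progression Using Neuroanatomical Markers). "This study included 18 CDR 0.5 subjects and 26 CDR 0 subjects", and the CDR 0.5 subjects were untreated. "The first 12 eigenvectors explained 75% of the variance in hippocampal shape". The MANOVA on these 12 gave F = 2.66 on 12 and 31 df, p = 0.014, and "effect size = 2.0". No other effect size for shape change appears in the document.

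Hypothesis 2 predicts equal rates of change in untreated and donepezil-treated DAT subjects, and slower change on the combination. Section h (Data Analysis) tests shape with a MANOVA on the eigenvectors of change. Section a gives the group sizes: 21 untreated, 38 to 47 donepezil, about 40 combination and 44 nondemented.

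**The concern.** The treatment question in Hypothesis 2 lies between DAT groups. The observed shape effect lies between DAT and normal ageing. The document reports no shape-change difference between differently treated DAT groups, and Preliminary Studies says only that the method might be sensitive to one. The power paragraph opens by introducing the testing of Hypothesis 2, so readers will take >85% as the power of the drug comparisons.

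Two things are at stake. A non-significant shape MANOVA between DAT groups could be read as evidence of no drug effect. And because part of Hypothesis 2 is a prediction of equality (untreated versus donepezil), a weak test would appear to confirm it.

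A second issue is that a distance estimated from 12 variables in 44 subjects is biased upward, and 2.0 is given with no interval.

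**Working it through.** **Inputs.** F = 2.66, df 12 and 31, 18 v 26 subjects (Preliminary Studies). Group sizes are from section a. Section e keeps a subset of eigenvectors that "accounts for ~75 % of the variance in hippocampal shape is used in group comparisons"; the preliminary study needed 12 for 75%, so p = 12 is carried over as an assumption. Alpha 0.05 is stated only for Hypothesis 1 and is assumed here. Contrasts are pairwise, without multiplicity adjustment.

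**1. Reproducing 2.0.** With N = 44:
- T² = F·p·(N−2)/(N−p−1) = 2.66 × 12 × 42/31 = 43.25
- D² = T²·N/(n₁n₂) = 43.25 × 44/468 = 4.07, so D = 2.02
- The same F gives p = 0.0141.

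The stated 2.0 is therefore the raw sample Mahalanobis distance, correctly computed.

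**2. Bias.** If there were no true difference, the expected D² would be (42/29) × 12 × 44/468 = 1.63. The unbiased estimate is 4.07 × 29/42 − 12 × 44/468 = 2.81 − 1.13 = 1.68, so D = 1.30. Inverting the noncentral F gives noncentrality limits of 1.36 and 52.1. Multiplied by 44/468 and square-rooted, these become 0.36 and 2.21. As a check, simulating a true D of 1.3 with 18 v 26 subjects gave a mean sample D² of 4.14 (root 2.04).

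**3. Power.** Noncentral F with p numerator df and noncentrality D²·n₁n₂/(n₁+n₂). The denominator df is n₁+n₂−p−1 for a two-group analysis. If the error covariance is pooled over all four groups (N = 143 to 152), it is (N−4)−p+1. Example: D = 0.5, 40 v 38, noncentrality 0.25 × 1520/78 = 4.87 on 12 and 65 df, power 21%. Four-group results are in brackets.

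| Distance | Combination (40) v donepezil (38–47) | Combination (40) v untreated (21) |
|---|---|---|
| 2.0 | >99% | >99% |
| 1.30 | 97–98% (98–99%) | 84% (89–90%) |
| 0.65, half of 1.30 | 35–40% (38–43%) | 24% (27%) |
| 0.5 | 21–23% (22–25%) | 15% (16%) |
| Distance needed for 85% | 1.01–1.07 (0.98–1.04) | 1.31 (1.23) |

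Donepezil versus untreated (38–47 v 21, two-group) has 23–25% power at 0.65.

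**4. Sensitivity to the eigenvector count (two-group model).** From 4 to 20 eigenvectors:
- The distance needed for 85% runs from 0.81 to 1.24 versus donepezil and from 1.03 to 1.54 versus untreated.
- Power at 0.5 runs from 15 to 40% versus donepezil and from 11 to 26% versus untreated.
- Power at 0.65 versus donepezil runs from 25 to 64%.
- Power at 1.30 versus untreated is 92% with 8 eigenvectors and 78% with 15.

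**The case against.** **The >85% reproduces, and bias correction hardly touches it.** This stands. At 2.0 every pair of groups exceeds 99%, and at 1.30 combination versus donepezil still has 97–98%. A reader might infer that the uncorrected 2.0 by itself invalidates the figure; it does not. The 84% versus untreated is not a clear failure either, since it moves to either side of 85% with the covariance model and the eigenvector count.

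**The power sentence never prints 2.0.** True. The link runs through the cited study, and the Progress Report does not appear in the document under that name. But 2.0 is the only shape-change effect size given. The sentence's other input, 0.5, does not rescue it for shape. Read as a single-variable effect in cross-sectional SD units with correlation 0.75, it becomes 0.5/√(2 × 0.25) = 0.71 on the change score. That gives 88–91% power for combination versus donepezil, but for one variable. Even a distance of 0.8 gives no more than 61% in the 12-variable, two-group MANOVA.

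**The wording may mean change over time, as with the 50 mm³ decrease.** Possible. Detecting change within subjects would then be what is powered, and that is still not a contrast between treatments.

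**A reader might infer that a drug must abolish about 80% of disease-related shape change to be detectable.** The documents do not support that. It divides 1.01–1.07 by the point estimate 1.30 (78–83%). At the upper confidence limit of 2.21 the share is 46–48%; at the lower limit of 0.36 no amount of slowing would suffice. The 1.3 also comes from CDR 0.5 subjects only, whereas this study includes CDR 1, so it is not an established ceiling.

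**Conclusion.** The point holds, as a mismatch between the effect used and the contrast tested; no stated number is miscalculated. The >85% for shape describes a difference the size of DAT versus nondemented and is not a power for the drug contrasts. With 12 eigenvectors and alpha 0.05, power for distances of 0.5 to 0.65 is about 21–43% for combination versus donepezil and 15–27% for combination versus untreated, over the two-group and four-group pooled analyses. No eigenvector count from 4 to 20 brings either distance to 85%. The 0.5 is taken here as a multivariate distance, which the document does not specify, and 0.65 is an illustration, not an estimate of any drug effect. An overall MANOVA that includes the nondemented group would not settle the matter, because it could be significant through disease alone.

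**What to change.** In section i, remove shape from the >85% statement, or say that it applies only to a difference as large as the one seen between DAT and nondemented subjects. Then state the between-treatment distance detectable with 85% power at the planned group sizes, with the assumed eigenvector count and alpha:

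- With 12 eigenvectors and alpha 0.05: about 1.0–1.1 for combination versus donepezil and 1.2–1.3 for combination versus untreated.
- Across 4 to 20 eigenvectors (two-group model): about 0.8–1.2 and 1.0–1.5.

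Also say on what scale the 0.5 is meant and whether it applies to shape. If the distance is translated into a share of disease-related change removed, label that an assumption and show its range, not a single percentage. Noting in Preliminary Studies that 2.0 is uncorrected, with 1.3 (0.4 to 2.2) beside it, would help but is optional.

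The cost is a few sentences, with no change to design or sample size. The drawback is that a stated figure becomes less favourable.
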